#### **4.4. End of Study Definition**

##### **End of Study Definition**

The end of study (EOS) is considered as the last visit (Follow-up Week 48 or early discontinuation) for the last participant in the study. With implementation of Protocol Amendment 5, the last visit for the last participant in the study may be up to Follow-up Week 72 (see Study Completion Definition below for rationale). The final data from the study site will be sent to the sponsor (or designee) after completion of the final participant visit at that study site, in the time frame specified in the Clinical Trial Agreement.

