1.2. Study Design

A target of 24 chronic HBV-infected male and female participants, 18-65 years (inclusive) of age

will be enrolled in Panels 1 and 2, approximately 12 participants in each panel. In Panel 3, a target of 4-6 chronic HBV-infected male and female participants will be enrolled.

- Panel 1 will consist of participants who are HBeAg positive and not currently treated.
- Panel 2 will consist of participants who are HBeAg negative and virologically suppressed by ETV, TD, or TAF treatment.
- Panel 3 will consist of participants who are HBeAg positive or negative and are either not currently treated or virologically suppressed by ETV or TD treatment.

The study will be conducted in 3 phases for all participants:

- A **screening phase** (4 to 6 weeks),
- An **open-label study intervention phase** (48 weeks),
- A **follow-up phase** (48 weeks). Note that the follow-up period will be extended up to an additional 24 weeks for participants who are receiving optional treatment with PegIFN- α 2a and who meet NA treatment completion criteria at the end of treatment with NA and PegIFN- α 2a to ensure all participants have at least one year of follow-up after NA treatment cessation.

The duration of individual participation will be up to 102 weeks for participants who stop NA treatment at the end of the open-label phase, or up to 126 weeks for participants who stop NA treatment during the follow-up phase.

Prior to Protocol Amendment 5, in Panels 1 and 2, participants were randomized in a 1:1 ratio within each panel to receive one of the following interventions (i.e., treatments) for 48 weeks:

- **Arm 1**, combination regimen JNJ-3989+JNJ-6379+NA:
 - 200 mg JNJ-3989 (SC injection Q4W, with the last injection at Week 44), and
 - 250 mg JNJ-6379 (tablets qd), and
 - NA: ETV, TD, or TAF (tablets qd)
- **Arm 2**, combination regimen JNJ-3989+NA:
 - 200 mg JNJ-3989 (SC injection Q4W, with the last injection at Week 44), and
 - NA: ETV, TD, or TAF (tablets qd).

As of Protocol Amendment 5, in Panels 1 and 2, participants who were previously randomized to Arm 1 had to stop JNJ-6379 treatment immediately but will still receive JNJ-3989 and NA – effectively joining Arm 2. New participants will enroll without randomization to Arm 2.

No participants were enrolled in Panel 3 before Protocol Amendment 5 was in effect. Therefore, all Panel 3 participants will enroll without randomization to receive the Arm 2 regimen.

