5. STATISTICAL ANALYSES

5.1. General Considerations

5.1.1. Analysis Phase

The analysis phases are defined in [Table 1](#) below. Note that the screening, open-label, and follow-up phases are non-overlapping and cover the entire study period. The optional PegIFN- α 2a treatment phase, in contrast, may overlap with both the open-label and follow-up phases.

Table 1: Analysis Phases Start and End Dates

Analysis phase	Start date	End date
Screening	The date of signing the informed consent	1 day before the first study agent intake (JNJ-3989 or JNJ-6379)
Open-label study intervention	Date of first study agent intake (JNJ-3989 or JNJ-6379)	Earliest of the following dates: 
 • Early discontinuation date for JNJ-3989 + 5 days^a • Study termination date • Max{ 
 • Date of last JNJ-3989 intake, • Date of Week 48 visit • } + 5 days^a • Cut-off date^b
Follow-up	End date of open-label phase + 1 day	Min (study termination date, study completion date, cut-off date ^b)
Optional PegIFN- α 2a treatment	Date of first PegIFN- α 2a intake	Min (Date of last PegIFN- α 2a intake + 5 days ^a , cut-off date ^b)

a : Addition of 5 days is only applicable for Adverse Events and Concomitant Medications.

b : Cut-off dates will be defined to match the prespecified timepoints for interim analyses, the primary analysis and the final analysis, respectively.

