5.2. Participant Dispositions

The number and percentage of participants who are screened, fail screening, and reason for that screening failure will be tabulated by study panel for the Screened Analysis Set.

The number and percentage of participants enrolled, enrolled and not treated, and reason for not being treated will be tabulated by study panel for the Enrolled Analysis Set.

Study disposition and treatment disposition will be summarized for the ITT Analysis Set, as described below.

An overview of the study disposition will be provided by analysis phase, study panel, and overall. The number and percentage of participants who completed or discontinued (or are ongoing [except the final analysis]) and the number and percentage of participants for each study discontinuation reason will be summarized.

An overview of the treatment disposition will be provided. The number and percentage of participants who completed or discontinued study treatment or were ongoing at the time of the IAs or primary analysis cut-off (except the final analysis) will be presented by analysis phase, study panel, and overall. The incidences of treatment discontinuation reasons will also be summarized by analysis phase, study panel, and overall.

A listing including information (i.e., study panel, the date of last study visit, the last analysis phase and time point [phase and week], the date of discontinuation and the reason) on participants who prematurely discontinue from the study and/or study treatment will be included. Information on NA discontinuation and/or re-treatment will also be included.

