5.4.2.5. Functional Cure

A participant will be defined as having achieved Functional Cure (FC) at a given time point during the FU phase if he/she has HBsAg seroclearance (as defined in Section 5.4.2.1) at that time point and has stopped all study interventions (including NA and PegIFN- α 2a) for at least 24 weeks without re-treatment.

Participants who discontinue treatment prior to Week 48 (except for JNJ-6379), or who withdraw from the study prior to the given time point, will be considered as non-responders for FC in this study. The CRF pages of ‘Treatment Disposition of JNJ-3989’, ‘Treatment Disposition of NA Treatment’, ‘Treatment Disposition for NA Re-Treatment’ and ‘Treatment Disposition for PegIFN-alpha2a’ will be checked to ensure all treatment actually stopped.

Subjects still in the study at a given time point but with missing HBsAg assessment at that time after implementation of LOCF (as described in Section 5.4.2.1), will be considered as non-responders.

Number and proportion of participants achieving FC will be summarized at 24, 36, and 48 weeks after stopping all study interventions (including NA and PegIFN- α 2a). Subjects who never reach such time points will be considered as non-responders.

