5.8. Interim Analyses

Two Interim Analyses (IA) may be performed: when all participants have completed Week 20 in the study intervention phase (or discontinued earlier) and when they have completed Week 72 (FU Week 24) in the follow-up phase (or discontinued earlier). These IAs will be performed by the sponsor to support interactions with health authorities, as well as to support internal decisions about additional studies and/or investigation of other combination regimens.

Both primary (when all participants have completed Week 48 or discontinued earlier) and interim analyses will be based on all data available at the predefined cut-off time points and may include data at later time points for those participants who have reached subsequent visits.

The final analysis will be performed when all participants have completed the last study visit (Follow-up Week 48) or discontinued earlier.

The overview of data domains and specific endpoints that will be provided for each analysis is presented in [Table 7](#).

Table 7: Overview of Times of Data Summaries and Analyses at Planned Interim, Primary and Final Analyses

	IA1 when all participants have completed Week 20	Primary Analysis when all participants have completed Week 48	IA2 when all participants have completed FU Week 24	Final Analysis when all participants have completed FU Week 48
DATA DOMAINS FOR ANALYSIS				
Subject Information				
Baseline & Demographic characteristics	X	X	X	X
Disposition and Study Populations	X	X	X	X
Extent of Exposure	X	X	X	X
Safety				
TEAEs, SAEs, AE of interest, fatal AEs, AEs causing treatment discontinuation	X	X	X	X
Laboratory Tests	X	X	X	X
ECG	X	X	X	X
Vital signs	X	X	X	X
Efficacy				
Primary efficacy endpoints		X	X	X
Secondary efficacy endpoints	X	X	X	X
Exploratory Endpoints	X	X	X	X
PK		X	X*	X*
Virologic breakthrough HBV	X	X	X	X
Flares: Viral, Biochemical, Clinical	X	X	X	X
Viral Genome Sequence Analysis		X	X	X

* If new data are available.

No DMC or Data Review Committee (DRC) is required for this study.

An Independent Flare Expert Panel (IFLEP) is appointed for this study to monitor ALT flares and make recommendations regarding flare management based on analysis of aggregate data. The IFLEP is composed of 3 independent medical experts with experience and expertise in hepatitis B and its treatment.

Further details on the IFLEP process will be provided in the IFLEP charter.

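### The final analysis and its data cut-off are still tied to Follow-up Week 48 although follow-up can now run to Follow-up Week 72, so on a literal reading some late functional-cure readouts could be cut off

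*SAP*

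**What the plan says.** The synopsis, Protocol section 9 and SAP 5.8 time the final analysis in the same way: "The final analysis will be performed when all participants have completed the last study visit (Follow-up Week 48) or discontinued earlier". The header in SAP Table 7 does not mention a last visit at all: "Final Analysis when all participants have completed FU Week 48".

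SAP Table 1 ends the follow-up phase at "Min (study termination date, study completion date, cut-off date"), and footnote b adds: "Cut-off dates will be defined to match the prespecified timepoints". That footnote names the final analysis alongside the interim and primary ones. The permission to use data beyond a cut-off (Protocol 9.5, SAP 5.8) is given for the primary and interim analyses only.

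Protocol Amendment 5 lengthened follow-up by up to 24 weeks for PegIFN participants who meet the NA completion criteria when NA and PegIFN end. Protocol 4.4 accordingly says that "the last visit for the last participant in the study may be up to Follow-up Week 72".

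SAP 5.4.2.5 reads functional cure at 24, 36 and 48 weeks after everything has been stopped, and adds: "Subjects who never reach such time points will be considered as non-responders". It makes no exception for a data cut-off.

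Other parts of the SAP assume that the extension is analysed:
- Table 2 has visit windows up to Follow-up Week 72.
- Section 5.5.6 uses the last follow-up visit for PegIFN participants who stopped NA during follow-up.
- The disposition summary in 5.2 counts participants who completed, discontinued "or are ongoing [except the final analysis"]), so nobody is expected to be ongoing by then.
- Section 5.6.1 lists cut-offs for the interim and primary analyses only.

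**The concern.** The extension exists "to ensure all participants have at least one year of follow-up after NA treatment cessation". Every version of the SAP (June 2022 to February 2024) is later than Protocol Amendment 5 (October 2021), yet the timing of the final analysis was not updated to match.

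Suppose the database were closed on the calendar date when the last participant reaches Follow-up Week 48. Table 1 would end follow-up on that date for anyone still in the extension, and no clause would bring the later visits back in. Off-treatment readouts not yet reached could then be counted as failures in people who are still under observation. Functional cure at 36 and 48 weeks is what is exposed; sustained HBsAg response and late flares would lose the same visits.

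**Working it through.** **1. Reproduce the plan's calendar.** Maximum participation is screening 6 + intervention 48 + follow-up 48 = 102 weeks, or 6 + 48 + 72 = 126 weeks with the extension. Both match SAP 1.2. Follow-up Week 48 is follow-up day 48 × 7 + 1 = 337 and study Week 48 + 48 = 96. Follow-up Week 72 is day 72 × 7 + 1 = 505 and study Week 120. Both match SAP Table 2.

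**2. Inputs.** PegIFN starts after the Week 40 biopsy and before Week 48 (SAP 1.2), taken here as Weeks 40 to 48. It lasts 12 or 24 weeks. NA is assumed to stop when PegIFN ends, which is the extension case. Readouts are k = 24, 36 and 48 weeks after the stop (SAP 5.4.2.5).

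**3. Readout week = start + duration + k, compared with Week 96.**

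| Course | Stop (week) | 24 weeks off | 36 weeks off | 48 weeks off |
|---|---|---|---|---|
| 12 weeks | 52–60 | 76–84, inside | 88–96, inside | 100–108, 4–12 past |
| 24 weeks | 64–72 | 88–96, inside | 100–108, 4–12 past | 112–120, 16–24 past |

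**4. Who is exposed.** The cut-off is a calendar date. A participant enrolled d weeks before the last one is at Week 96 + d on that date, so a readout is lost only if d < stop + k − 96. The largest value is 72 + 48 − 96 = 24 weeks.

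**5. Effect of last observation carried forward (LOCF).** SAP 5.4.2.1 allows HBsAg to be carried forward by up to 12 weeks at these readouts. The gap is stop + k − 96 − d. It exceeds 12 only for the 48-week readout after a 24-week course, when d < stop − 60, that is d below 64 − 60 = 4 up to 72 − 60 = 12 weeks. The other gaps in the table are within the limit, if LOCF applies to them.

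**6. After the fix.** With follow-up counted to Week 120, the latest readout is 72 + 48 = 120, so every readout in the table is reachable.

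**7. Size per participant.** One misclassified participant moves the functional-cure rate by 1/12 = 8.3 points in a panel of 12, or 1/24 = 4.2 points of 24. The documents do not give the number of late NA stoppers. Assuming 0 to 4 of 24 misclassified, the range is 0 to 16.7 points.

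**8. Sensitivity.** The biopsy window of ±4 weeks allows a start at Week 36, and 36 + 12 + 48 = 96 is not past the cut-off. In the other direction, the protocol's follow-up schedule counts from the last JNJ-3989 dose (Week 44). That puts Follow-up Week 48 at Week 92 and adds 4 weeks to every shortfall. The 24-week readout would then also be missed for stops after Week 68, by up to 72 + 24 − 92 = 4 weeks.

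**The case against.** The strongest reply is that the intent is clear. Protocol 9 and SAP 5.8 speak of the last study visit, Amendment 5 moved that visit, and the bracketed Follow-up Week 48 is a label left behind. The extension windows, the special rule in SAP 5.1.2 for visits from follow-up day 352 onward, section 5.5.6 and the absence of an ongoing category all fit a final analysis held after the extension. On that reading the minimum in Table 1 resolves to study completion and nothing is lost. This is the more likely intent, and section 5.2 in particular supports it. But the Table 7 header and footnote b of Table 1 do not say so, and a prespecified lock date should not depend on inference.

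Three further limits stand:
- LOCF may cover gaps of 12 weeks or less; the SAP does not say whether LOCF or the rule on time points never reached prevails.
- Participants who never stop NA are non-responders under any cut-off.
- A participant who stops NA at Week 48 but stays on PegIFN is outside the extension and may miss the 48-week readout whatever the final cut-off, so the fix below does not help there.

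A reader might infer that the plan discards extension data, or that functional cure at 36 and 48 weeks will be understated. The documents do not support either: they contradict themselves on timing, and any loss also needs late enrolment together with a late NA stop.

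**Conclusion.** The stated timing of the final analysis and its cut-off contradicts the end of study in Protocol 4.4 and the SAP's own extension windows, and it should be corrected. The possible harm is limited to extension participants enrolled within about 24 weeks of the last participant. For them, on the SAP's calendar with PegIFN starts at Weeks 40 to 48, the 48-week readout and, after a 24-week course, the 36-week readout could be scored as failures. Only the 48-week readout after a 24-week course can fall outside the LOCF limit. The 24-week readout, which is the protocol's definition of functional cure, is not affected on this calendar.

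The number affected is unknown and may be zero, because neither enrolment dates nor the number of late NA stoppers is given. The study is descriptive and its primary endpoint is at Week 40, so no test, power figure or primary result changes. A reader might also set the promised year against 48 weeks of follow-up (48 × 7 = 336 days); that is a separate wording question and adds nothing to this point.

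**What to change.** - In the synopsis, Protocol 9, SAP 5.8 and Table 7, time the final analysis by each participant's own last scheduled visit: Follow-up Week 48, or up to Follow-up Week 72 for those in the extension, with early discontinuations counted as finished.
- Set the final cut-off in SAP Table 1 to that date and bring the cut-off sentence in SAP 5.6.1 into line with it.
- In SAP 5.4.2.5, state that a time point unreached only because of a data cut-off is not scored as a failure, and say whether LOCF or the rule on time points never reached takes precedence.
- Reconcile the two starting points for counting follow-up weeks (last JNJ-3989 dose in the protocol schedule, Week 48 in SAP Table 2), so that the cut-off has one meaning.

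The cost is wording and a final lock up to 24 weeks later, at an end of study that the protocol already defines. No visit, sample size or analysis method changes.

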6. SUPPORTING DOCUMENTATION

6.1. Appendix 1 List of Abbreviations

AE	adverse event
ALT	alanine aminotransferase
ANCOVA	analysis of covariance
AST	aspartate aminotransferase
ATC	anatomic and therapeutic class
AUC	area under the curve
BMI	body mass index
BSA	body surface area
CHB	chronic hepatitis B
CI	confidence interval
CL	total systemic clearance
Cmax	maximum concentration
CRF	case report form
CSR	Clinical Study Report
CTCAE	Common Terminology Criteria for Adverse Events
CV	coefficient of variation
DMC	Data Monitoring Committee
DPS	Data Presentation Specifications
ECG	electrocardiogram
eCRF	electronic case report form
ETV	entecavir
F (%)	absolute SC bioavailability
FAS	full analysis set
FDA	Food and Drug Administration
HBcrAg	hepatitis B core-related antigen
HBeAg	hepatitis B e antigen
HBsAg	hepatitis B surface antigen
HBV	hepatitis B virus
ICH	International Conference on Harmonisation
ITT	intent-to-treat
IQ	interquartile
IVRS	interactive voice response system
IWRS	interactive web response system
LLOQ	lower limit of quantification
LOCF	last observation carried forward
MedDRA	Medical Dictionary for Regulatory Activities
MRD	minimum required dilution
NA	nucleos(t)ide analogs
NAb	neutralizing antibodies
PD	pharmacodynamic(s)
PegIFN- α 2a	pegylated interferon alpha-2a
PI	principal investigator
PK	pharmacokinetic(s)
PP	per protocol
SAE	serious adverse event
SAP	Statistical Analysis Plan
SD	standard deviation
SMQs	standardised MedDRA queries
TEAE	treatment-emergent adverse event
Tmax	time to maximum concentration
US NCI	United States National Cancer Institute
V	volume distribution
Vz	volume of distribution based on terminal phase
Vz/F	apparent volume of distribution based on terminal phase after extravascular administration

WHO World Health Organization
WHO-DD World Health Organization Drug Dictionary

6.2. Appendix 2 Changes to Protocol-Planned Analyses

No change from protocol-planned analyses.

6.3. Appendix 3 Demographics and Baseline Characteristics

The number of participants in each analysis set will be summarized and listed by study panel and overall. In addition, the distribution of participants by country, and site ID will be presented unless otherwise noted.

6.3.1. Demographics

Table 8 presents a list of the demographic variables that will be summarized by study panel and overall for the ITT.

Table 8: Demographic Variables

Continuous Variables:	Summary Type
Age (years)	
Weight at baseline (kg)	
Height at baseline (cm)	
Body Mass Index (BMI) (kg/m ²)	
Number of drinks containing alcohol (weekly period)	
Type of substance (beer, wine, distilled spirits) duration in months derived as = (stop date – start date +1)/30.4375; rounded to 1 decimal	Descriptive statistics (N, mean, standard deviation [SD], median and range [minimum and maximum], and IQ range).
Categorical Variables	
Age ([18 years - ≤ 30 years, > 30 years -≤ 45 years, > 45 years-≤ 60 years, > 60 years])	
Sex (male, female, undifferentiated)	
Race ^a (American Indian or Alaska Native, Asian, Black or African American, Native Hawaiian or other Pacific Islander, White, Multiple)	
Ethnicity (Hispanic or Latino, not Hispanic or Latino)	
BMI ([underweight <18.5 kg/m ² , normal 18.5-<25 kg/m ² , overweight 25-<30 kg/m ² , obese >=30 kg/m ²])	
History of tobacco use (Yes, No)	
Type of substance use (beer, wine, distilled spirits) : current, former, never	

^aIf multiple race categories are indicated, the Race is recorded as 'Multiple'

6.3.2. Baseline Characteristics

Table 9 presents a list of the baseline characteristics variables that will be summarized by study panel and overall for the ITT and Safety analysis set (only if ITT and Safety Analysis sets are different).

Table 9: Baseline Characteristics Variables

Continuous Variables	Summary Type
HBV history	
Duration of infection (years) = (treatment start date – date of HBV infection +1)/365.25; rounded to 1 decimal	
Time since HBV diagnosis (Years) = (treatment start date – date of HBV diagnosis+1)/365.25; rounded to 1 decimal	
Duration of NA at baseline (years)	
HBV viral activity and serology parameters	

Continuous Variables	Summary Type
HBeAg at baseline in IU/mL and log10 IU/mL (for HBeAg positive participants only at study entry)	
HBsAg at baseline in IU/mL and log10 IU/mL	
HBV DNA at baseline in IU/mL and log10 IU/mL	
HBV RNA at baseline: values in copies/mL and log10 copies/mL	
HBcrAg at baseline in log U/mL	
HBsAg Antibody (Anti-HBs) at baseline in mIU/mL and log10 mIU/mL	
Fibrosis score	
HBV intrahepatic viral parameters	
Proportion of HBsAg+ hepatocytes at baseline, derived as number of HBsAg+ hepatocytes * 100 / total number of evaluated hepatocytes	Descriptive statistics (N, mean, standard error [SE], standard deviation [SD], median and range [minimum and maximum], and IQ range).
Proportion of cccDNA-positive hepatocytes, derived as number of cccDNA-positive hepatocytes * 100 / total number of evaluated hepatocytes	
Proportion of pgRNA-positive hepatocytes, derived as number of pgRNA-positive hepatocytes * 100 / total number of evaluated hepatocytes	
pgRNA/cccDNA ratio (transcriptional activity)	

 • Proportion infected with active transcription • <1.6 cccDNA copies and active transcription • Infected without HBV transcription: silenced hepatocytes • Non-infected hepatocytes (LLOD 1.6 copies/cell) 	
RNA levels (copies / cell)	
Proportion of immune cells at baseline	
Categorical Variables	Summary Type
HBV history	
Mode of HBV infection: Sexual transmission, intravenously injectable drug use, blood transfusion, Hemophilia-associated injection, occupational exposure, mother to child transmission, unknown and other	
Treatment history: not currently treated, virologically suppressed	
History of IFN-alpha : Yes, No	
History of Lamivudine, Telbivudine, Adefovir : Yes, No	
Has never received HBV treatment (only for currently not treated participants): Yes, No	
Type of NA at study entry (only for virologically suppressed participants): TD, TAF, ETV	

Continuous Variables	Summary Type
HBV viral activity and serology parameters	Frequency distribution with the number and percentage of participants in each category.
HBeAg status at study entry: positive, negative	
HBsAg category at baseline (IU/mL): < 500, < 1,000, < 10,000, ≥ 10,000	
HBV DNA category at baseline (IU/mL): < LLOQ Target detected (TD) or not detected (TND), < LLOQ TD, < LLOQ TND, < 60, < 2,000, < 20,000, < 100,000, ≥ 100,000	
HBV RNA category at baseline (copies/mL): TND, < Limit of Detection (LOD), < LLOQ, < 1,000, ≥ 1,000	
HBcrAg category at baseline (log U/mL): < 3, ≥ 3 - < 4, ≥ 4	
HBsAg Antibody (Anti-HBs) status at baseline: Positive, Negative	
HBsAg Antibody (Anti-HBs) category at baseline (mIU/mL): < 10, ≥ 10	
HBeAg Antibody (Anti-HBe) status at baseline: Positive, Negative	
Baseline ALT toxicity grade according to DAIDS	
Baseline ALT categorization: ≤ 1.0xULN, > 1.0xULN to <2.5xULN, ≥ 2.5x	
Stage of liver fibrosis: F0, F1, F2	

